| The assessment of relationship will be reported on the case report forms /worksheets by an investigator who is a qualified physician according to his/her best clinical judgment, including consideration of the above elements. |                                                 |                                                                                                                                                                                                                                                                                                                                                                                                                                                                                                                                                                                                                                                                                                                                                                               |  |
| Record one of the following                                                                                                                                                                                               |                                                 | Use the following scale of criteria as guidance (not all criteria must be present to be indicative of a Merck product relationship).                                                                                                                                                                                                                                                                                                                                                                                                                                                                                                                                                                                                                                   |  |
| Yes, there is a reasonable possibility of Merck product relationship.                                                                                                                                                     |                                                 | There is evidence of exposure to the Merck product. The temporal sequence is reasonable. The AE is more likely explained by the Merck product than by another cause.                                                                                                                                                                                                                                                                                                                                                                                                                                                                                                                                                                                                          |  |
| No, there is not a reasonable possibility Merck product relationship                                                                                                                                                      |                                                 | Subject did not receive the Merck product OR temporal sequence of reasonable OR there is another obvious cause of the AE. (Also entered if the AE onset relative to administration of the Merck product is not for a subject with overdose without an associated AE.)                                                                                                                                                                                                                                                                                                                                                                                                                                                                                                         |  |

### **7.3.5 Sponsor Responsibility for Reporting Adverse Events**

All Adverse Events will be reported to regulatory authorities, IRB/IECs and investigators in accordance with all applicable global laws and regulations.

## 8.1 STATISTICAL ANALYSIS PLAN

### 8.2 Statistical Analysis Plan Summary

Overall response rate (ORR) and the 95% confidence interval of that estimate will be obtained through binomial distribution theory, using the ITT population, with a one-sided endpoint, for the primary endpoint. Progression free survival, overall survival, landmark one-year progression free survival, landmark one-year overall survival will be obtained by Kaplan-Meier method.

The adverse events will be tabulated descriptively, by grade. All AEs will be summarized by system organ class and preferred term. Listings and summary tables will be provided. Separate data listings and summaries will be presented for all serious adverse events (SAEs) and deaths.

The correlative study tests will be analyzed as an exploratory assessment, or as part of a separate correlative protocol.

### 8.3 Statistical Analysis

#### *Study population definitions*

The primary endpoint, ORR, will be estimated, along with a with one-sided 95% confidence interval, counting evaluable patients (the “combination treatment population”) getting at least one per-protocol dose of IL-2, using binomial distribution theory.

The response assessment and safety assessment populations are defined for the analyses as follows:

*FIGURE 7: Population definitions*

| name                                                 | description                                                                   |
|-------------------------------------------------------------|--------------------------------------------------------------------------------------|
| Intent to treat (ITT) population
(ITT efficacy analysis) | Eligible and registered                                                              |
| Ever-treated population
(Safety evaluation population)   | At least one dose of pembrolizumab                                                   |
| Combination treatment population                            | At least one dose of pembrolizumab (start of block B1) and at least one dose of IL-2 |

|                                  |                                                                                          |
|----------------------------------|------------------------------------------------------------------------------------------|
|                                  | (usually indicating a start of block B2, and usually at least 4 doses of pembrolizumab). |
| Combination threshold population | At least 6 doses of pembrolizumab and at least 10 doses of IL-2 (In any block).          |

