#### 3.3 Secondary Objectives & Hypotheses

(1) **Objective:** ORR for patients getting at least 4 doses of pembrolizumab and one dose of IL-2:

(2) Objective: ORR for, and for patients completing at least 6 doses of pembrolizumab and at least 20 doses of IL-2 (designated as “completing at least half of the treatment per-protocol”).

(3) **Objective:** This is an exploratory safety objective: OS will be not demonstrably inferior to contemporary subjects with matched clinical risk features from PROCLAIM database observed OS (using  $p \geq .05$ )

**Hypothesis:**  $H_0$ : OS[1-year] is more than 20% lower than matched controls

$H_A$ : ORR is same or better (using  $p \geq .05$ )

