##### **Rationale for assessment of the fraction of patients with at least half the doses**

In the randomized study of nivolumab versus everolimus, the median progression free survival was 4.6 months, corresponding to what would be about 6.5 blocks of 21 days. Thus, 6 pembrolizumab doses is of interest, because it corresponds to a duration of PD-1 inhibition for which an overall survival benefit was demonstrated in patients with metastatic clear cell renal cancer. The total number of pembrolizumab doses planned in this study is 12. Six doses, whether all in a row, or in the unusual circumstance of interruption and then later administration, would be a cumulative dose of interest for that reason. (Motzer 2015)

The total number of doses needed to have an IL-2 response is not firmly defined, despite decades of study. In the randomized study of high dose IL-2 vs low dose IL-2 and interferon, for which a statistically superior overall survival difference was observed in the former arm,

the dose delivery of 68% of 28 doses, that is 19 doses was used, for cycle #1. Later cycles were not summarized, the majority of patients did not get later cycles. (McDermott 2015) In the 2016 ASCO meeting, a threshold of at least 18 high dose IL-2 doses was identified as a marker of better response outcomes (Chow et al. 2016)

Thus 6 doses of pembrolizumab covers about the same dose duration of nivolumab, and 20 doses of IL-2 define threshold levels of drug delivery for which survival impact has been demonstrated in phase III randomized immunotherapy trials in patients with metastatic clear cell kidney cancer. The patients in those trials are not anticipated to be a group of patients which can be directly compared to the patients in this trial, because of the shifting availability other drugs, and contemporary patient selection. (Motzer 2015)

For this purpose, a prospective definition of a achieving a minimal dose delivery will be set as at least 6 pembrolizumab doses and at least 20 IL-2 doses. Each patient will be assessed for this, not the overall averages. Other definitions can be considered; this feasibility concept is one that is used in conjunction with the efficacy part of the primary objective, the ORR estimate.

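### No population in section 8 matches secondary objective 2: the objective requires at least 20 IL-2 doses, the SAP's only dose-threshold population requires 10

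*Combined protocol and SAP*

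**What the plan says.** Section 3.3, objective (2), asks for ORR "for patients completing at least 6 doses of pembrolizumab and at least 20 doses of IL-2", and labels this group as having completed half or more of the protocol treatment. The part of section 4.4.4.1 on patients with at least half the doses gives the same rule as a prospective definition: "a minimal dose delivery will be set as at least 6 pembrolizumab doses and at least 20 IL-2 doses". It is a patient-level criterion: "Each patient will be assessed for this, not the overall averages". The supporting argument there ends with the statement that "20 doses of IL-2 define threshold levels of drug delivery for which survival impact has been demonstrated".

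Section 8.3, Figure 7, lists four populations: ITT, ever-treated, combination treatment (at least one dose of each drug) and combination threshold. The last is defined as "At least 6 doses of pembrolizumab and at least 10 doses of IL-2 (In any block". Figure 8 in section 8.5 repeats the 6/10 rule as a column of the adverse-event table. The short paragraph on secondary analyses at the end of section 8.4 refers back to the Figure 7 populations and names the threshold population among them.

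**The concern.** The objective and the analysis populations give different IL-2 cut-offs (20 and 10) beside the same pembrolizumab cut-off (6). The word threshold is attached to 20 in the rationale and to 10 in the SAP. Someone programming from section 8 would report ORR in the 6/10 set. Someone programming from section 3.3 would build a 6/20 set that section 8 does not define. Both could present the result as the dose-delivery subgroup.

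Dose delivery is one of the two feasibility issues named in section 4.4.4.1, and it is to be read alongside the response rate when deciding on further development. In a small, open-label, single-arm trial, two thresholds left open also allow a choice between them after the data are seen.

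**Working it through.** **Planned doses.** Pembrolizumab: 4 blocks × 3 doses = 12, which reproduces the total stated in section 4.4.4.1. IL-2: 20 doses in each of two blocks (section 2.2), or eight admissions (section 5.2.2, Timing of Dose Administration) × 5 doses = 40.

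**Share of plan under each rule.**

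| Rule | Pembrolizumab | IL-2 |
|---|---|---|
| Objective 2 and section 4.4.4.1 (6/20) | 6/12 = 50% | 20/40 = 50% |
| Figures 7 and 8 (6/10) | 6/12 = 50% | 10/40 = 25% |

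Only 6/20 fits the label of half the treatment.

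**Support for the number.** The rationale cites 68% of 28 doses in a randomised IL-2 trial (0.68 × 28 = 19.04, stated as 19) and a meeting report in which "a threshold of at least 18 high dose IL-2 doses was identified as a marker of better response outcomes". The supporting figures are thus 19 and 18; the 20 is the section's own definition. Both lie above 10.

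**What the bracketed block qualifier in Figure 7 can mean.**

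- *Doses counted across blocks:* a total of 10 or more. Every 6/20 patient qualifies, plus those with 10–19.
- *Ten or more in at least one IL-2 block:* a total of 20 over two blocks forces at least 10 in one of them, so again every 6/20 patient qualifies. The extra patients are those with 10 or more in one block but a total below 20.
- *Ten or more in each IL-2 block:* the total is then at least 20, but a patient with 18 + 6 = 24 meets 6/20 and fails this rule.

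No reading gives the 6/20 set. The first is the most natural: a block holds three or four pembrolizumab cycles, so 6 pembrolizumab doses cannot fall in a single block and the row must count across blocks.

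**Can a patient fall between the rules?** On schedule, the sixth pembrolizumab dose is the third of block 2, by which time 20 IL-2 doses have been planned. A patient who stops there after missing one to ten IL-2 doses meets 6/10 but not 6/20. Section 2.2 allows doses to be omitted for safety, and section 4.4.2 says most pilot patients received 18–20 of 20 planned. That pilot was IL-2 alone, so it shows the gap is plausible but does not give its size.

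**Illustrative effect on ORR.** Let n patients meet 6/20 with r responders, and let m more meet only 6/10. Under either of the first two readings the 6/10-set ORR lies between r/(n+m) and (r+m)/(n+m). The documents give none of n, r or m. Assume n = 12 and r = 6, so ORR = 50% (exact 95% CI 21–79%).

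| m | None of the m respond | All of the m respond |
|---|---|---|
| 0 | 50% | 50% |
| 1 | 6/13 = 46% | 7/13 = 54% |
| 2 | 6/14 = 43% | 8/14 = 57% |
| 4 | 6/16 = 38% (CI 15–65%) | 10/16 = 63% (CI 35–85%) |
| 6 | 6/18 = 33% | 12/18 = 67% |

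With r = n/2 the largest shift is m/(2(n+m)). For m = 1, 2, 4, 6 that is 5.6, 10.0, 16.7 and 21.4 points if n = 8, and 2.9, 5.6, 10.0 and 13.6 points if n = 16.

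**The case against.** The strongest reply is that nothing conflicts. Section 3.3 specifies the objective 2 subset completely, so its ORR can be computed without a Figure 7 row. The secondary-analysis paragraph lists its populations as inclusions, not as a closed list, and does not assign objective 2 to any of them. Objective 1, "ORR for patients getting at least 4 doses of pembrolizumab and one dose of IL-2", has no literal row either, so Figure 7 may simply be a separate list. The rationale adds: "Other definitions can be considered; this feasibility concept is one that is used in conjunction with the efficacy part of the primary objective". Ten doses are also half of one block's 20, which may be where the number came from.

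Part of this stands. The documents do not say that the 6/10 row was meant to implement objective 2. A reader might infer from the shared 6 and the shared word threshold that 10 is a misprint for 20, but the rule appears in both Figure 7 and Figure 8, and the text settles neither origin nor intent. Nor can one say that section 8 forbids a 6/20 analysis.

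What does not fall is the gap. The openness to other definitions neither names 10 nor withdraws 6/20, and the half-a-block explanation is not in the documents. If Figure 7 is a separate list, section 8 still has no population for objective 2 and offers a near match that answers a different question.

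It is also fair that both subsets are selected on exposure after baseline, in a trial of up to 26 patients, and are descriptive. Even the extreme estimates at m = 6 lie inside the 21–79% interval for 6/12. That limits the consequence but does not remove the inconsistency.

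**Conclusion.** Wrong as written, with limited reach. Objective 2 and its rationale require 20 IL-2 doses, the SAP's only dose-threshold population requires 10, and no section 8 population matches the objective. That follows directly from the text and the dose arithmetic.

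Statements about the size of the difference are conditional. Treating the 6/10 set as the 6/20 set plus extra patients depends on either of the first two readings of the block qualifier. The ORR ranges depend on assumed n, r and m, and if m = 0 the two sets coincide.

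Two stronger readings are not supported. A reader might infer that Figure 8 is also wrong, but objective 2 concerns ORR and no section sets a 6/20 population for adverse events. A reader might also infer that the trial's decision is at risk. However, objective 2 carries no test or cut-off, and the primary ORR test, the Simon design and the toxicity boundary do not use the threshold population. The effect is confined to secondary and feasibility reporting.

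**What to change.** Reconcile section 3.3 and section 4.4.4.1 with Figures 7 and 8 before analysis. This is a matter of analysis-set definitions only and touches no dosing rule.

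- **If the objective stands as written:** add a 6/20 population to Figure 7 and state in section 8.4 that objective 2's ORR is computed in it. Keep 6/10 only as a separately named set, with its reason given and the block qualifier clarified. Figure 8 need not change.
- **If the sponsor intends 6/10 to govern objective 2:** amend sections 3.3 and 4.4.4.1 to say so, give a reason for 10, and drop the label of half the treatment, since 10 of 40 is a quarter.

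The cost is SAP or protocol wording, applied to dosing data already recorded; no new data or patients are needed. The drawbacks are that the 6/20 set may be smaller than the 6/10 set, so its ORR may be less precise, and that if 6/10 were also replaced in Figure 8, patients with 10–19 IL-2 doses would drop out of that adverse-event column.

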#### 8.4 Planned primary reporting analyses

Analysis: Overall response rate ORR is defined with confirmation of the response status CR or PR among the combination treatment population patients; the binomial estimate and its one-sided 95% confidence interval will be reported.

Analysis: Overall survival (OS) of ITT patients counting from the eligible date to death from any cause, or censored on end of known follow up, either within this study or in the PROCLAIM registry.

Analysis: Progression-free survival (PFS) of ITT patients from the confirmed eligible date to the first occurrence of disease progression or death, from any cause, or lost to follow up, whichever is earliest; or censored at last follow-up during study.

Kaplan-Meier method will be used for OS as well as PFS analysis.

The Simon minimax two-stage design (Simon, 1989) with a 10% type I error and 90% power will be used to test the null hypothesis that overall response rate (CR+PR)  $\leq 0.20$  versus the alternative hypothesis of overall response rate  $>0.45$ . In the 1st stage, 15 patients will be treated. If 3 or fewer respond, the trial will be terminated. If 4 or more respond, an additional 9 evaluable patients (the “combination treatment population”) will be studied in the 2nd stage (a total of  $n=24$  evaluable patients). If the total number responding is less than or equal to 7, the drug is rejected. This design has an expected sample size of 18 patients with a probability of early termination of 0.65.

The overall total number of patients, counting patients with at least one dose of IL-2 administered, will be up to  $n =26$ . This will accommodate replacement of subjects who are in the intent-to-treat(ITT) population, but not part of the main developmental objective of the study, which is the combination treatment population.

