### 3.1 OBJECTIVES & HYPOTHESES

#### 3.2 Primary Objective & Hypothesis

(1) **Objective-Efficacy portion:** Estimate the frequencies of disease response so as to be a basis to commit to more development of this schedule. Note that this is framed broadly, with the understanding that the decision to commit to further development of the schedule includes a variety of feasibility endpoints.

The ORR will be defined as the CR + PR patients, with confirmation of the response status (numerator), among those ever treated (denominator). **Hypothesis:** For the efficacy portion  $H_0$ : ORR is  $<20\%$  and  $H_A$ : ORR is  $>45\%$ . Thus, a 45% ORR (CR + PR) would be considered of definite interest for further development, contingent on the feasibility assessment as well, as part of the decision. With a Simon 2-stage design, 24 evaluable patients are needed.

**Objective –Safety portion:** The co-primary endpoint of adverse event and serious adverse event tabulation comprises a critical portion of the ultimate assessment of feasibility for moving forward with additional and directly comparative trials using this regimen. There are known frequencies of these (referencing the respective monotherapy prescribing information documents) for which this tabulation can be compared. The relatively small sample size of this series versus those series typically would prevent specific hypothesis testing.

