#### **Subject Replacement Strategy**

Subjects with an apparent CR after B1, 9 weeks of pembrolizumab, may be treated with up to 12 doses pembrolizumab, but no IL-2, at the investigator discretion. These will be replaced (up to the total enrollment target of 26).

Subjects with clinical events after initial B1 dose of pembrolizumab, but then later not meeting usual criteria for treatment with IL-2 at the point in time of the B2W2 IL-2 start, despite having previously met them before start – for example new onset rapid atrial fibrillation – may continue on pembrolizumab at treating physician discretion, up to 12 doses. These will be replaced (up to the total enrollment target of 26).

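### The primary response rate has three different denominators, so the reported estimate and its lower limit depend on which section is followed

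*Combined protocol and SAP*

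**What the plan says.** The current text gives the primary ORR three denominators.

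- **Ever treated.** Section 3.2 counts responders "with confirmation of the response status (numerator), among those ever treated (denominator"). In Figure 7 this set needs one pembrolizumab dose.
- **ITT.** Section 8.2 obtains the ORR and its interval "using the ITT population, with a one-sided endpoint, for the primary endpoint". In Figure 7 this set is everyone eligible and registered, and the table labels it as the efficacy analysis set.
- **Combination treatment.** Section 8.3 counts evaluable patients "getting at least one per-protocol dose of IL-2, using binomial distribution theory", and 8.4 repeats that "ORR is defined with confirmation of the response status CR or PR among the combination treatment population patients". Figure 7 defines the set as "At least one dose of pembrolizumab (start of block B1) and at least one dose of IL-2".

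The short subsection after 8.4 on secondary analyses lists both the ever-treated and the combination treatment populations as secondary. Section 3.3 also makes "ORR for patients getting at least 4 doses of pembrolizumab and one dose of IL-2" a secondary objective, a group almost the same as the 8.4 primary population.

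The two-stage rule appears only in 8.4. It ties the 9 second-stage patients and the total of 24 evaluable patients to the combination treatment population. For stage 1 it says only that 15 patients are to be treated.

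The number 26 has two meanings. In the Trial Summary (1.0) and the Subject Replacement Strategy it is total enrollment; in 8.4 it counts patients given at least one IL-2 dose.

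**The concern.** IL-2 starts only in block 2, after about nine weeks of pembrolizumab, so membership of the combination treatment population is decided by events after treatment begins. The plan expects the sets to differ. A patient with an apparent CR after block 1 may continue pembrolizumab "but no IL-2, at the investigator discretion. These will be replaced (up to the total enrollment target of 26"), and patients who no longer meet IL-2 criteria are handled the same way. A confirmed block-1 complete responder who never gets IL-2 is a responder under 3.2 and 8.2, but is in neither numerator nor denominator under 8.4.

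ORR is the stated basis for further development; in 3.2, "a 45% ORR (CR + PR) would be considered of definite interest for further development". If the population is not fixed in advance, an analyst could defend any of three estimates and three intervals after seeing the data.

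**Working it through.** **1. The plan's own design.** Inputs from 8.4: p0 = 0.20, p1 = 0.45, n1 = 15 (stop at 3 or fewer), n = 24 (reject at 7 or fewer).

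- Early termination at p0: P(X1 ≤ 3 | 15, 0.20) = 0.648 (stated 0.65).
- Expected n: 15 + 9 × (1 − 0.648) = 18.2 (stated 18).
- P(go | p) = Σ over x = 4 to 15 of P(X1 = x | 15, p) × P(X2 ≥ 8 − x | 9, p). This gives 0.0835 at p = 0.20 (limit 0.10) and 0.900 at p = 0.45 (target 0.90).

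An exhaustive search returns the same design as minimax. The design arithmetic is right.

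**2. Estimate and interval.** The documents do not say how many patients will miss IL-2. Assume 2, with 24 IL-2 recipients and everyone registered also treated, so ever treated = ITT = 26. The exact one-sided 95% lower limit is the 5% quantile of Beta(x, n − x + 1).

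| Responders / n | Situation | ORR | Lower limit |
|---|---|---|---|
| 8/24 | combination treatment | 33.3% | 17.8% |
| 8/26 | neither of the other two responds | 30.8% | 16.3% |
| 10/26 | both are confirmed block-1 responders | 38.5% | 22.6% |
| 7/24 | combination treatment (drug rejected) | 29.2% | 14.6% |
| 9/26 | same trial plus two block-1 responders | 34.6% | 19.4% |

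From the same 8 responders among IL-2 recipients, the reported lower limit lies below or above 20%. The 7/24 trial is a rejection under 8.4. Counted as ever treated it is 9/26, for which the plan states no cut-off. The 8/24 limit is already below 20% because the test uses 10% and the interval 5%; that is a separate matter.

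**3. Carrying the cut-off to a larger set.** With stage 1 kept at 3/15 and go still requiring more than 7 responders, the formula in step 1 with 10 or 11 second-stage patients gives a type I error of 0.099 at n = 25 and 0.116 at n = 26. The latter exceeds the planned 10%.

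**4. How often the decision itself differs.** The loss rates are assumptions: 10% or 20% of patients are non-responders who never reach IL-2, and a further 0% or 4% are early complete responders without IL-2. IL-2 recipients respond at 20% or 45%. Enroll 26, keep sequences with at least 24 IL-2 recipients, and apply the rule to the first 15 and 24 ever treated and to the first 15 and 24 IL-2 recipients (400,000 sequences per scenario). The decisions differ in about 2% to 4% of trials at ORR 20% and about 4% to 5% at ORR 45%. These figures are conditional: at the 20% loss rate, only 3% to 8% of 26-patient enrollments reach 24 IL-2 recipients.

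**The case against.** The strongest reply is that 8.4 already settles the decision rule. The cut-offs appear nowhere else, and 8.4 calls the combination treatment population the main developmental objective. Section 8.3 equates it with evaluable patients, and even 3.2 asks for 24 evaluable patients. Since 24 minus 9 is 15, stage 1 must also mean 15 evaluable patients. Most of this stands. A reader might infer that the go/no-go rule is undefined or the Simon design invalid. The documents do not support that: the rule is correct and largely anchored, with one loose phrase in stage 1.

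A reader might also infer that leaving out patients who never reach IL-2 inflates the ORR. That does not follow. Dropping early failures raises it and dropping block-1 complete responders lowers it, and the plan gives no rate for either.

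Simulating with no limit on enrollment gives decision differences of 3% to 24%. That range should not be used, because the Trial Summary and the Subject Replacement Strategy cap total enrollment at 26. With 24 IL-2 recipients, at most 2 patients can then be without IL-2.

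The secondary objective in 3.3 is coherent if 3.2 is read as primary, so it is a consequence of the same conflict and not a further one. The plan also already includes an ever-treated analysis, although the same sentence lists combination treatment as secondary, contrary to 8.3 and 8.4. Finally, this is a feasibility trial that is not meant to be definitive. That limits the consequences but does not tell an analyst which denominator is primary.

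**Conclusion.** The point holds as a contradiction in the primary analysis. Sections 3.2, 8.2 and 8.3/8.4 name three distinct populations for the same ORR, with no order of precedence. What is open is mainly the estimate and its interval, plus the stage 1 wording and the two meanings of 26.

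With two patients assumed not to reach IL-2, the estimate for 8 responders among 24 IL-2 recipients ranges from 30.8% to 38.5%, and the lower limit from 16.3% to 22.6%, on both sides of the null. The effect on the decision is small: about 2% to 5% of trials that reach 24 IL-2 recipients within 26 enrolled, under assumed loss rates. No direction of bias is claimed. ITT and ever treated were not separated numerically; they differ only by patients registered and never dosed, and the plan gives no figure for that.

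**What to change.** Name one primary population and use it for both stages, the point estimate and the interval. Make 3.2, 3.3, 8.2, 8.3, 8.4 and the secondary-analysis subsection after 8.4 agree.

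The choice most consistent with 8.4 is the combination treatment population:

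- Name it in 3.2 and 8.2, and remove it from the list of secondary populations.
- State stage 1 as 15 evaluable combination-treated patients.
- Reconcile the near-identical objective in 3.3.
- Report ever-treated and ITT ORR as sensitivity analyses, with the number of patients who did not reach IL-2 and the reasons.

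If ever treated or ITT is chosen instead, apply the rule to exactly the first 15 and first 24 such patients without replacement, or recompute the cut-offs; keeping more than 7 at n = 26 gives a type I error of 0.116. Power stays at 0.90 for 24 patients only if the 45% target is meant for that population. If 45% is meant only for IL-2 recipients, power must be restated.

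In either case define 26 once, as total enrollment or as IL-2 recipients. With the combination population the cost is wording plus one table and no extra patients.
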